12.8 Safety Analyses

The safety analyses will be performed at least five times, 1- when a minimum of one third of the initially enrolled patients have completed their LAU-7b (or placebo) treatment period and corresponding safety information is available, 2- when at least two thirds of the initially enrolled patients have completed their LAU-7b (or placebo) treatment period, 3- at the time of final analysis subsequent to the planned database lock on 15Sep2021 for the pilot part of the study, 4- when at least half of the expansion's enrolled patients have completed their LAU-7b (or placebo) treatment period, and 5- at the time of final analysis (after completion of the expanded enrolment and database lock). Safety analyses will be performed on the safety population (those patients who receive at least one dose of study drug). Blinded safety data will be assessed by the DSMB at regular meetings. The DSMB may request unblinding of patients for safety concerns in addition to receiving the unblinded interim analyses results. Like it was the case for the pilot portion of the study, the study expansion will be double blinded to the Investigators, patients and sponsor's staff until the revised end of the study, unless circumstances require unblinding.

Safety and tolerability will be assessed by the following:

- Adverse events described and categorized according to the MedDRA, version 16 or more recent.
- Clinically relevant changes from baseline in vital signs
- Clinically relevant changes from baseline in directed physical examinations
- Clinically relevant changes from baseline in safety laboratory assessments (hematology with differential count, biochemistry, and urinalysis).

12.8.1 Adverse Events

Adverse events will be tabulated with reported incidences by treatment, number of patients that presented adverse events by treatment, serious adverse events by treatment, number of adverse events by body system and by treatment. Summaries will be presented by MedDRA system organ class and preferred term.

For the purpose of analyses and tabulations, AEs will be classified as pretreatment AEs and TEAEs. More specifically: Pretreatment AE are those that started after consent signature and before the first dose of study

drug and did not increase in severity. TEAE are those that increased in severity or that was appeared at or after the first dose of study drug and before or at the last follow-up, on Day 60, or earlier if early terminated. Post-treatment AEs are not collected in this study. For AEs with missing or incomplete start dates, if there is no clear evidence that the AEs started before or after the first dose of study drug, then the AEs will be classified as TEAEs.

AE summary tables will be presented for TEAE only and will include the following: All TEAEs, TEAEs by relationship, TEAEs by maximal severity, TEAEs leading to treatment discontinuation, Serious TEAEs and fatal TEAEs. All AEs, including pre-and post-treatment AEs, will be presented in individual patient data listings.

The number and percentage of patients with at least one AE, as classified by preferred term and system organ class, will be summarized for each treatment group. For these summaries, patients with multiple events will be counted only once per preferred term. AEs will also be summarized by severity and relationship to study drug. At each level of summarization, the event with the highest level of severity or strongest drug relationship will be presented.

All AEs must be listed. In addition, detailed listings will be provided for patients who die, experience a SAE, or discontinue the study because of an AE. These listings will include treatment, patient's age, duration of follow-up, amount of fenretinide received, and time since last intake.

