In the RESOLUTION safety population (all randomized patients who took a minimum of one dose of study medication, n=232), a total of 798 adverse events (AEs) were experienced by 191 out of 232 patients. Almost all AEs (99.2%+) were treatment emergent (TEAEs) in both treatment arms. The majority of the subjects (52 to 55%) in both treatment arms experienced "not related or unlikely related" events to the study treatment, 20 to 26% experienced "possibly related" events, a minority (4.3%) experienced "related" events and 17-18.5% of patients did not report adverse events. The majority of the subjects (56 to 60%) experienced mild to moderate events while 10 to 16% of the patients had severe adverse events and a minority (10-11%) had life-threatening events, mostly worsening of COVID-19 respiratory failure. A total of 24 treatment-emergent fatalities occurred in the study, spread similarly between the two arms of the study; none of the fatalities were deemed to be related to the study treatment.

The independent study DSMB reviewed twice in a blinded and unblinded manner the safety information from the pilot portion and recommended to continue the study unchanged until its conclusion. So far in the Phase 3 extension, The DSMB met once and recommended to continue the study unchanged.

Across most body systems, the incidence of TEAEs was comparable between the LAU-7b arm and the placebo arm, supporting the conclusion that LAU-7b has a good safety profile in COVID-19 patients, even for body systems known to be typical of fenretinide AEs, such as gastrointestinal, eye disorders and even skin disorders despite a slightly higher incidence in the LAU-7b arm, mostly mild dry skin events. The vast majority of treatment-emergent SAEs (TESAE) were related to the COVID-19 condition and no SUSAR was reported to Health Authorities. The safety profile remains well balanced across the treatment arms when sorted by Health Status subgroup.

Efficacy Summary:

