7.1.2 Primary Efficacy Endpoint

The revised primary efficacy endpoint is the proportion of patients requiring mechanical ventilation AND/OR deceased (all causes) by Day 60, compared between the active and control (placebo) arms of the study using the 7-point ordinal scale described above.

Justification for the main Efficacy Variable and the revised Primary Efficacy Endpoint

LAU-7b is proposed to act through a multi-prong approach against COVID-19 disease. It is hypothesized that these effects will reduce the odds of aggravation for the at-risk population that is under observation/admitted at the hospital for the COVID-19 disease. This will translate in a higher proportion of patients that recover and are discharged earlier from the hospital compared to those treated with the SOC alone + placebo. The use of the 7-point Ordinal Scale proposed by the World Health Organization for COVID-19 clinical trials is ideally suited for establishing the proportion of patients requiring invasive mechanical ventilation (and this includes ECMO) AND/OR deceased (all causes) (WHO Ordinal Scale scores 6-7 inclusively) as primary endpoint, particularly if assessed regularly during the course of the study. The time course of the COVID-19 disease is quite short but its complications are devastating and entail a huge burden on caretakers. This efficacy variable and the proportion of patients requiring mechanical

LAU-7b for the treatment of COVID-19 disease in Adults

¹ Patients receiving up to 6L/min with a low-flow device can also qualify as an Ordinal Scale "4" if they have a pre-existing health condition (COPD, heart failure, for example) that causes higher oxygen supplementation needs and if the Investigator judges that the patient is NOT in respiratory failure. Other patients are subject to the <4L/min threshold.

ventilation AND/OR deceased (ordinal scale scores 6-7 inclusively) by Day 60, coined here as the revised primary efficacy endpoint, will permit both an overall picture of the impact of LAU-7b on patient outcomes, and a clinically meaningful assessment of the impact of LAU-7b on the proportion of patients avoiding the invasive mechanical ventilation and/or death.

In addition, changes in the health status depicted by the Ordinal Scale category changes will permit to derive several secondary endpoints listed below.

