8.3 Study Drug Discontinuation and Withdrawal of Patients

Patients should discontinue permanently the study drug in the event of any of the following (Since a low LAU-7b dose is used in this study, no dose reductions are planned):

- 1. If a patient is escalated to invasive mechanical ventilation preventing the administration of the study medication intact;
- 2. Occurrence of a SAE deemed related to the study drug that is a life-threatening adverse reaction or one resulting in prolonged non-COVID-19 disease-related hospitalization;

LAU-7b for the treatment of COVID-19 disease in Adults

² When a factor that may potentially affect renal function by hemodynamic mechanisms is known or suspected on admission (Ex: dehydration), it is recommended to rule out a possible renal impairment by addressing the issue whenever possible (Ex: rehydration) and reassessing CrCL prior to signing the ICF.

- 3. If the patient, Investigator, or Laurent determines that it is not in the best interest of the patient to continue treatment;
- 4. If a patient is serially and persistently noncompliant with study procedures and/or assessments, the investigator or the sponsor may withdraw the patient from further treatment;
- 5. A patient's treatment is unblinded by the Investigator;
- 6. If a female patient has a confirmed pregnancy (with the exception of a pregnancy resulting from *in-vitro* fertilization), this should be immediately reported to the Medical Monitor and Laurent Pharmaceuticals (within 24 hours awareness) and the patient shall discontinue the study drug. Pregnancy, whether in a patient or in a partner of a patient should be followed up until conclusion, with an assessment of child health at birth:
- 7. Considering the safety observed so far in the study, patients showing possible kidney impairment as depicted by either:
 - a. An increase from screening in serum creatinine of 0.5 mg/dL or 2x the screening value if the serum creatinine was within normal range at screening and the calculated CrCL was \geq 30 ml/min;
 - b. An increase of serum creatinine $\geq 2x$ the screening value if the screening value was above the normal range and the calculated CrCL was ≥ 30 ml/min.
- 8. Notwithstanding that the study so far confirms the lack of a particular drug-related liver toxicity, patients showing possible liver impairment as assessed with the liver safety algorithm based on the Drug Induced Liver Injury (DILI) algorithm, described in Section 11.4

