11.1.1.1 Adverse Event Severity

The Investigator must determine and record the severity of all serious and non-serious AEs. The Common Terminology Criteria for Adverse Events (CTCAE), Version 4.03, (Cancer Therapy Evaluation Program website; available at: http://ctep.cancer.gov/protocolDevelopment/electronic_applications/ctc.htm; accessed 01 December 2015) should be used for grading the severity of AEs. AEs of CTCAE Grades 4 and 5 should be documented as "life-threatening."

The severity of an AE that does not appear in the CTCAE scale should be determined according to the definitions below. Clinically significant laboratory tests should be recorded as AEs in the patient's source documents and e-CRF.

Severity will be assessed according to the following criteria:

Classification	Definition
Mild (Grade 1)	Mild level of discomfort and does not interfere with regular activities
Moderate (Grade 2)	Moderate level of discomfort and significantly interferes with regular activities
Severe (Grade 3)	Significant level of discomfort and prevents regular activities
Life-threatening (Grade 4)	Any adverse drug experience that places the patient, in the view of the investigator, at immediate risk of death

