11.1.3 Serious Adverse Events

SAEs are generally any AEs that result in one or more of the following:

- Fatal (death, regardless of cause, that occurs during participation in the study or occurs after participation in the study but within 30 days post-study (Day 90), and is suspected of being a delayed toxicity due to administration of the study drug);
- Is immediately life threatening (i.e., presents an immediate risk of death at the time of the AE, not an AE that hypothetically might have caused death if it were more severe);
- Requires or prolongs inpatient hospitalization*;
- Causes persistent or significant disability/incapacity;
- Is a congenital anomaly/birth defect;
- Other important medical events that may not be immediately life threatening or result in death or hospitalization but, based upon appropriate medical judgment, are thought to jeopardize the patient and/or require medical or surgical intervention to prevent one of the outcomes defining an SAE**.
- *An inpatient hospitalization is defined as an admission for any length of time. In this specific case of COVID-19 patients already hospitalized, other hospitalization for routine or planned clinical procedures, prolongation of hospitalization for any COVID-19-related adverse change in the patient's condition, or for "social" reasons, should not be considered an AE and should not be reported as a SAE.
- ** While prolongation of hospitalization and/or transfer to Intensive Care Unit per se shall not be considered a AE/SAE, if invasive mechanical ventilation/ECMO is started, the cause for it is an important medical event and therefore reaches the criteria of seriousness to be reported as a SAE.

Definition of Life-Threatening Adverse Experience:

An adverse experience is life threatening if the patient was at immediate risk of death from the event as it occurred (i.e., it does not include a reaction that, had it occurred in a more serious form, might have caused death). For example, drug-induced hepatitis that resolved without evidence of hepatic failure would not be considered life threatening, even though drug-induced hepatitis can be fatal.

Definition of Disabling/Incapacitating Experience:

An adverse experience is incapacitating or disabling if the experience results in a substantial and/or permanent disruption of the patient's ability to carry out normal life functions.

Medical Monitor:

[name], MD

Laurent Safety Line: [contact]

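### The headline serious, fatal and severity adverse-event rows include the primary-endpoint events, so if LAU-7b works they can mask an excess of other serious events; a second version of the tables is needed

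*Protocol*

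**What the plan says.** Protocol Section 12.8.1 lists the TEAE tables: "All TEAEs, TEAEs by relationship, TEAEs by maximal severity, TEAEs leading to treatment discontinuation, Serious TEAEs and fatal TEAEs". It also plans summaries by system organ class and preferred term, and detailed patient listings of deaths, serious events and discontinuations due to adverse events. It does not describe a version that separates the primary-endpoint events.

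The primary endpoint in Section 7.1.2 is the "proportion of patients requiring mechanical ventilation AND/OR deceased (all causes) by Day 60". The same events enter the safety tables as follows:

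- **Ventilation/ECMO.** Section 11.1.3: "if invasive mechanical ventilation/ECMO is started, the cause for it is an important medical event and therefore reaches the criteria of seriousness".
- **Death.** Section 11.1.3 lists "Fatal (death, regardless of cause, that occurs during participation in the study" among the seriousness criteria. The reporting text in Section 11.1.3.1 instead sets deaths from disease progression apart.
- **Time window.** TEAEs run from first dose to "before or at the last follow-up, on Day 60, or earlier if early terminated", nearly the same window as the endpoint.
- **Severity.** Section 11.1.1.1: "AEs of CTCAE Grades 4 and 5 should be documented as" life-threatening, the top class.
- **Discontinuation.** Section 8.3 stops study drug permanently "If a patient is escalated to invasive mechanical ventilation preventing the administration of the study medication intact".

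The pilot summary in Section 5.4.2.1 shows that this happens in practice: "The vast majority of treatment-emergent SAEs (TESAE) were related to the COVID-19 condition". It also counts 24 treatment-emergent deaths and describes the life-threatening events (10-11% of patients) as mostly worsening respiratory failure.

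The SAP Addendum lists only efficacy tables among those affected.

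**The concern.** In a trial whose efficacy endpoint is ventilation or death, a working drug lowers the count of serious and fatal TEAEs through efficacy alone. If the drug also causes other serious events, the two effects offset each other in the any-event row, and a reader sees similar totals. Section 5.4.3.2 says the extension is meant to be confirmatory and might support an Emergency Use Authorization. In that setting the overall serious-event rate by arm will be one of the first safety figures read. A second table without disease-progression events would show whether level totals mean no added harm, or added harm offset by benefit.

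**Working it through.** **Inputs from the documents.** Design rates 7% (placebo) and 0% (LAU-7b), 132 per arm, two-sided Fisher exact test, alpha 0.05, power at least 90% (Protocol Section 12.1). Pilot, Health Status 3 or 4: 5/72 ventilated on placebo, 0/76 ventilated or dead on LAU-7b (Section 5.4.2.1).

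**Plan's own figure.** Exact binomial enumeration of the Fisher test at 132 per arm, 7% v 0%, gives power 0.906, so the stated sample size reproduces. The pilot comparison 5/72 v 0/76 gives p = 0.025, as stated.

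**Size of the overlap.** Expected endpoint patients are 132 × 0.07 = 9.24 on placebo and 132 × 0 = 0 on LAU-7b. The plan's other scenario (231 per arm, 4% v 0%, Section 12.2) gives the same number: 231 × 0.04 = 9.24.

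**Assumptions.** Let q be the rate of other serious TEAEs in both arms and d the rate of drug-caused serious TEAEs on LAU-7b. Neither is in the documents, so ranges are used. The sources are taken as independent.

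- LAU-7b, either version: 1 − (1 − q)(1 − d)
- Placebo, all events: 1 − (1 − q)(1 − 0.07)
- Placebo, endpoint events removed: q

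Example, q = 5%, d = 5%: LAU-7b is 1 − 0.95 × 0.95 = 9.8%. Placebo is 1 − 0.95 × 0.93 = 11.7% with endpoint events and 5.0% without. The difference is −1.9 points in the first version and +4.8 points in the second.

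**Chance that LAU-7b shows the higher count** (exact binomial, 132 per arm, no test involved):

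| q | d | All events | Endpoint events removed |
|---|---|---|---|
| 3% | 3% | 10% | 84% |
| 3% | 5% | 25% | 95% |
| 3% | 7% | 46% | 99% |
| 5% | 3% | 13% | 80% |
| 5% | 5% | 27% | 92% |
| 5% | 7% | 46% | 97% |
| 10% | 3% | 18% | 72% |
| 10% | 5% | 31% | 85% |
| 10% | 7% | 47% | 92% |

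At d = 7% the all-event row is level by construction, because d then equals the efficacy effect. At d = 10% the chances are 69-74% with endpoint events and 98-99.9% without, so a larger excess is less well hidden.

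**What the other planned rows show.** Suppose the 7% excess falls in one system organ class with a 1% background: 1 − 0.99 × 0.93 = 7.9% v 1.0%. A two-sided Fisher test on that row would show a significant LAU-7b excess with probability 0.73. Spread the same 7% over five unrelated terms, 1.4% v 0% each, and the probability is about 0.01 per row. No adverse-event test is planned; these two figures only indicate how visible each pattern would be.

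**Which tables are affected.** Serious and maximal severity: endpoint events throughout follow-up. Fatal: deaths, subject to reconciling Sections 11.1.3 and 11.1.3.1. Discontinuation: only ventilation while still on drug. Dosing ends by Day 14 (Section 9.3), so events on Days 15-60 cannot enter it.

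**The case against.** **The all-event row is not biased.** A reader might infer that the safety comparison is confounded with efficacy. It is not: arms are randomized, and the row validly compares net serious harm. Preventing ventilation is a real reduction in serious events. This objection stands. The second table answers a different question; it does not correct an error.

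**Other rows can reveal harm.** A reader might also infer that only the any-event row is large enough to show an excess. The 0.73 figure for a single organ class shows otherwise. The relationship table and the listings help too. The relationship table, however, rests on investigator causality, for which underlying disease is a recognised alternative explanation (Section 11.1.1.2), and listings give no rate by arm. A diffuse excess could still be missed.

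**The magnitude is assumed.** This stands: q and d are not in the documents, and the built-in advantage disappears if LAU-7b has no effect on the endpoint.

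**A simple exclusion could hide harm.** Dropping every cause of ventilation would remove a drug-caused event that led to intubation. Recording also thins after intubation: Section 11.1.1 keeps ventilation complications and some acute-care laboratory changes out of the eCRF, and Section 11.2 ends laboratory entry. Both points stand. The first shapes the exclusion rule; the second is a limitation to state.

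**The full plan is not visible.** Protocol Section 12 defers detail to the SAP, and the main SAP of 29SEP2023 is not among the documents. It may contain this split.

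**Conclusion.** The overlap follows from Protocol Sections 7.1.2, 11.1.3 and 12.8.1, and the pilot summary bears it out. At the design rates it puts about 9 extra placebo patients in the any-serious row. For a background of 3-10% and a drug-caused excess of 3-7%, the chance that LAU-7b shows the higher count is about 10-47% in the all-event row and 72-99% once endpoint events are removed. This rests on the assumed 7% v 0% effect, on independence, and on rates the documents do not give.

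The planned safety tables are valid but incomplete: they measure net harm and can mask a diffuse excess of other serious events. The documents do not support saying that every endpoint event is counted again in all four tables, since the discontinuation table is touched only by ventilation on Days 1-14. Nor do they show that no split exists anywhere in the plan, since the main SAP cannot be seen. The additional tables are a cheap and worthwhile improvement.

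**What to change.** First check whether the SAP of 29SEP2023 already contains such a split. If not:

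1. In Section 12.8.1 keep the all-event tables. Add a second version of the serious, fatal, maximal-severity and discontinuation tables, excluding only events classified as COVID-19 progression leading to ventilation/ECMO or death.
2. Keep in the second version any event judged related or possibly related, and any ventilation or death from a non-COVID cause.
3. Classify by a written rule, applied by reviewers without treatment codes. The SAP Addendum says results were first released on 14MAR2024, so flagging before lock is no longer possible; label the tables as added after that release.
4. State that the safety conclusion rests on both versions.
5. Reconcile Sections 11.1.3 and 11.1.3.1 on deaths from disease progression, because the content of the fatal table depends on it.

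The cost is one written rule, a classification exercise and four repeat tables. Serious-event follow-up reports already call for causality and evolution notes (Section 11.1.3.1). The downsides are the judgement on which events to flag, and possible undercounting of other events in ventilated patients because their eCRF recording is limited. State the second as a caveat under the new tables.

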12.8.2 Clinical Laboratory Assessments

Safety laboratory variables (e.g., hematology, biochemistry, and urinalysis results) will be presented in SI units, if available, at each time point using descriptive statistics (mean, standard deviation, median, minimum, and maximum).

